² When we designed the survey, we had not yet outlined the details of the multi-site project, so we asked for general information related to self-administered mindfulness protocols. For the purpose of the multi-site project we used only a portion of all the information provided by the answers of mindfulness practitioners, however we believe that the unused information may help other mindfulness researchers design more rigorous studies on the topic.

³ This process was done by the first author, however it is possible to infer how the simplification was done by comparing the files with all exercises (i.e., List of the exercises) and the one where similar exercises were merged (i.e., Mindfulness clusters MULTI-SITE; see https://osf.io/br86s/).

compassion break (5 votes) and loving kindness meditation (3 votes) for 'acceptance' (See Mindfulness clusters MULTI-SITE at https://osf.io/br86s/).

We then cross-referenced our set of self-administered mindfulness exercises with the list of 20 popular meditation techniques that Matko et al., (2019) detailed by consulting 637 meditators with an online survey. By retaining the exercises that were present in both approaches we arrived at this final list of self-administered mindfulness exercises: Body scan, mindful breathing, mindful walking and loving-kindness meditation. We decided to test these four mindfulness exercises in the multi-site project described below.

Study 2: The multi-site project

Hypothesis

We hypothesized that participants allocated to any one of the experimental (mindfulness) conditions would experience lower levels of self-reported stress compared to participants allocated to an active control conditions⁴.

Additionally we explored effects on the dimensions of pleasure, arousal and dominance of any of the experimental conditions as compared to the active control conditions. Similarly, we also explored the role of neuroticism in reducing levels of stress of individuals for the above mentioned conditions.

Methods

Materials

All materials used in the study, including the ethics (IRB) approval documents of all the sites involved in the project and the meditations scripts are available on our OSF page (https://osf.io/6w2zm/), the analysis code instead can be found on the GitHub repository of

⁴ Participants who end up in the control group will have an equal chance of listening to an excerpt of one the three stories that we selected for the present study.

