Given these aims, we modeled a sequential design with maximum *N* where the data collection continues until either the threshold for compelling evidence is met or the maximum *N* is reached. Initially, forty-one labs indicated interest in the project, we expect to have up to 30 data-collecting labs. Each lab was expected to collect data of at least N = 70 participants, with a stopping *N* at 120 (translating to *Min* = 420 and *Max* = 720 participants per condition). We intended to be able to detect an effect size of *d* = 0.20; here we modeled the true value to vary between labs by repeatedly (for each simulation) drawing from a normal distribution, $\delta \sim N(0.20, 0.05)$, with a 95% probability that the effect size falls between *d* = 0.10 and 0.30.

The present study aimed at testing the effectiveness of four stand-alone interventions using a between-subjects adaptive group design, where upon hitting a threshold of compelling evidence in one condition, the plan was to allocate the rest of the participants into other conditions where this has not been the case yet. The design analysis, however, assumed a conservative scenario with equal *N* across all conditions, therefore, simplifying the computations to a single between-subjects *t*-test scenario.

The results (see Figure 1) show that, given the assumed design, the probability of the test to arrive at the boundary of compelling evidence (BF = 10 or 1/10) was .79 (.72 at H_1 and .07 erroneously at H_0). The probability of terminating at maximum N of 720 per condition was .21; .05 of showing some evidence for H_1 (BF > 3), .13 of being inconclusive (3 > BF > 1/3), and .03 of showing evidence for H_0 (BF < 1/3). For the test of a single condition against controls, the sequential design is expected to be 27% more effective than collecting a fixed

maximum N per lab, with the average N at stopping point (*BF* boundary and maximum N) at 526. Even conservatively assuming a balanced-N situation, the informativeness of the design thus appears to be adequate and the use of adaptive design is likely to further enhance informativeness and/or resource efficiency. Figure 1 shows the results of the simulation of the sequential design with 10000 iterations.

Figure 1. Design analysis for the sequential bayesian design with maximum N

Procedure

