Participants accessed the experiment via a Qualtrics link. They were provided detailed information about the study (see "Participants Information Sheet" included in the IRB package, https://osf.io/6w2zm/) and were then asked to provide consent prior to participating. Each participant was asked to take part in the survey using a smartphone with headphones or earphones attached, not a computer or laptop, because one experimental condition includes mindful walking and, participants being randomly allocated to conditions, we needed to ensure that everyone would be equally capable to perform the mindfulness activity. To know if this condition was verified we included a question in which we asked participants whether they started the survey from a device other than a smartphone; if they answered negatively,

we asked them to exit the survey and to restart it, this time using a smartphone with headphones or earphones attached.

Participants were also asked to sit in a quiet place such as a room where they could not be disturbed for 20 minutes. After providing informed consent, they were asked to complete the Neuroticism subscale of the IPIP - 5 NEO Domains (IPIP, 2021) to assess the level of neuroticism. Examples of items were "I often feel blue" or "I am filled with doubts about things". Participants could answer a 5-points scale (1 = *Very inaccurate*, 2 = *Moderately Inaccurate*, 3 = *Neither Inaccurate nor Accurate*, 4 = *Moderately Accurate*, 5 = *Very Accurate*). We estimated the scale reliability (i.e., internal consistency) using the omega coefficient. Assuming a unitary-factor model, the reliability estimate in the present sample was $\omega_u = x$.

After the completion of the neuroticism measure, participants were randomly allocated to one of the five conditions⁶. In each condition, participants were presented with a different 15-minutes recording. The four audio files of the mindfulness exercises and the three audio files of the stories of the non-mindful active control condition were recorded by a certified meditator, to keep the voice constant across conditions. Following a brief description of the mindfulness conditions and of the three different stories of the non-mindful active control condition.

Body scan. In body scan, participants were invited to "scan" their parts of the body. Every time the mind wandered, participants were invited to bring back the awareness and the attention to the part of the body they were "scanning".

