To assess whether any of the chosen mindfulness exercises were more effective than the randomly sampled control conditions to reduce stress in participants, we planned to conduct a sequential design. We sampled participants until a Bayes Factor threshold for compelling evidence was met or until a maximally feasible number of participants was collected (Schönbrodt et al., 2017). Unlike in the frequentist approach, the aim of this procedure was not the control of error rates, but to gauge the relative support provided by the present data in favor of one of two competing hypotheses, H_1 and H_0 . In the frequentist approach, the practice of adjusting the sampling plan after peeking at the data would have increased the Type 1 error rate, but in the Bayesian approach, the data collection could be stopped anytime without having any consequences on the interpretation of the Bayes Factor (Rouder, 2014). We divided our analysis workflow into confirmatory and exploratory. The sequential testing was tied to the confirmatory analysis phase while the exploratory analyses had no role in the decisions related to sampling.

Confirmatory analyses

As the aim of the present study was to assess the effectiveness of four stand-alone mindfulness interventions without any aspirations to draw broad inferences about mindfulness intervention in general, we planned to carry out four independent comparisons with the active controls. Therefore, we carried out four independent-samples Bayesian t-tests to determine whether there was a difference between each mindfulness exercise and the active control condition. We employed a two-tailed test using a non-informative JZS Cauchy prior for the alternative hypothesis with a default *r*-scale of $\sqrt{2}/2$ (Rouder, Speckman, Sun, Morey, & Iverson 2009). To account for the hierarchical nature of the data, we compared the condition means using a Bayesian mixed-effects model that involved a random intercept for lab and for different stories used in the non-mindful active control condition.

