⁷ Each time we did so, we generated a file in Rmarkdown that we uploaded on the OSF project page. Similarly, we generated a Rmarkdown file, twice a week, to document how many participants were collected for each site and how many participants were assigned to each experimental group.

⁸ The maximum number of participants was set to 120k, where k is the number of sites that took part in the study, and 120 was the maximum number of participants that each site committed to collect.

⁹70 is the minimum number of participants that we requested to each site to collect to be considered for authorship

Date: 22 March 2022; Swansea University (UK) & Université Grenoble Alpes (France)

thus performed three different Bayesian *t*-tests for each dimension of the Self-Assessment Manikin scale (pleasure, arousal and dominance) comparing our experimental conditions with the control condition. We then looked at The Bayes Factor to establish whether the data favored H_1 or H_0 . Similarly as we did for the confirmatory analyses we compared the condition means using a Bayesian mixed-effects model that involved a random intercept for lab and for different stories used in the non-mindful active control condition to account for the hierarchical nature of the data.

To check whether neuroticism moderated the effects of the four experimental conditions on stress, we compared the model with the interaction to the model with only the main effects (using the lmBF function) and we reported the corresponding BF. If the model with the interaction was preferred to the model with only the main effects of a BF of 10 or more, we would have solid evidence of the moderation of neuroticism on stress. We computed the Markov chain Monte Carlo chain (MCMC) to estimate parameters through the posterior function, in this way for each condition we were able to assess whether there were differences in stress levels for people with high, average, or low neuroticism scores.

Dealing with careless or insufficient effort responder

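### The neuroticism read-out is described as stress differences within each condition, so it does not give the exercise-minus-control effect by neuroticism level that the moderation question needs

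*Combined protocol and SAP*

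**What the plan says.** The Hypothesis section of Study 2 announces the topic as exploratory: "we also explored the role of neuroticism in reducing levels of stress of individuals for the above mentioned conditions". The Exploratory analyses section states the question as one about effects: "To check whether neuroticism moderated the effects of the four experimental conditions on stress".

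Two steps follow there.

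- **Test.** The interaction model is compared with the main-effects model by lmBF. The decision rule is "If the model with the interaction was preferred to the model with only the main effects of a BF of 10 or more", which the plan would take as solid evidence of moderation.
- **Read-out.** MCMC samples are drawn from the posterior, so that "for each condition we were able to assess whether there were differences in stress levels for people with high, average, or low neuroticism scores".

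High, average and low are not defined. No exercise-minus-control difference by neuroticism level is named, and nothing says how a positive overall interaction would be traced to one exercise. The Procedure section places the marker before allocation: "After the completion of the neuroticism measure, participants were randomly allocated to one of the five conditions". It is therefore a proper baseline moderator.

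**The concern.** Moderation means that the exercise-minus-control difference changes with neuroticism. The read-out, taken at its word, compares people at different neuroticism levels inside one condition. That is prognostic information: anxious people score as more anxious, whatever they listened to. Seeing high scorers more stressed than low scorers in the body-scan arm says nothing about body scan unless the same gradient in the control arm is subtracted.

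At stake is what the secondary report can say. If the overall BF reaches 10, the reader will want to know which exercise, for whom and in which direction, and the planned read-out does not answer. If the BF does not reach 10, five tables of neuroticism differences may still be printed, since the read-out is not made conditional on the BF.

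**Working it through.** **Inputs.** Arm sizes come from the Bayesian design analysis: 30 labs × 70 / 5 = 420 and 30 × 120 / 5 = 720 per condition, which reproduces the plan's figures. Monitoring starts at 100 per group (Confirmatory analyses). The target effect is d = 0.20. The documents give no figure for the neuroticism analysis and no neuroticism-STAI correlation, so r = .2 to .5 is an assumption.

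**1. Size of the within-arm contrast with no moderation.** In SD units of STAI, the difference between +1 SD and −1 SD neuroticism is 2r: 0.4 SD at r = .2 and 1.0 SD at r = .5. That is two to five times the target effect, with every exercise effect constant across neuroticism.

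**2. How often it appears in all five arms.** For one arm the noncentrality is r√(n−2)/√(1−r²). The probability that the 95% interval excludes zero follows from the noncentral t distribution, and the fifth power gives all five arms. At r = .2:

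| n per arm | noncentrality | one arm | all five arms |
|---|---|---|---|
| 100 | 2.02 | .516 | .037 |
| 420 | 4.17 | .986 | .933 |
| 720 | 5.47 | .9998 | .999 |

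Simulation agrees (.929 at 420 and .999 at 720). At r = .3 the 100-per-arm figure is about 49%; at r = .3 to .5 with 420 or more per arm it is 100%. In the same simulations at 100, 420 and 720 per arm, the exercise-versus-control slope difference excluded zero in 3% to 6% of trials, as it should.

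**3. What the planned BF does in that situation.** With a common slope of 0.5 SD, no moderation, and a BIC approximation to the BF (not lmBF; no lab or story intercepts), the interaction BF reached 10 in 0% of runs and favoured no interaction by 10 or more in 100%, at both 420 and 720. The planned test separates prognosis from moderation; the read-out does not.

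**4. Joint BF against one BF per exercise.** Assume one exercise's slope differs from all the others by δ (residual SDs per SD of neuroticism). Under BIC, BF ≥ 10 requires the likelihood-ratio statistic to exceed q ln N + 2 ln 10, where q is the number of interaction terms. The statistic is approximately noncentral χ² on q degrees of freedom. Its noncentrality is 0.8nδ² for the five-arm model (q = 4, N = 5n) and nδ²/2 for one exercise against control (q = 1, N = 2n). At δ = 0.2:

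- n = 420, joint: threshold 4 × 7.650 + 4.605 = 35.2, noncentrality 13.4, probability 3%. Per exercise: threshold 6.733 + 4.605 = 11.3, noncentrality 8.4, probability 32%.
- n = 720, joint: threshold 37.4, noncentrality 23.0, probability 15%. Per exercise: threshold 11.9, noncentrality 14.4, probability 64%.

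Simulation of the joint BF gave 2% and 14%. At δ = 0.3 the pairs are 43% against 84%, and 91% against 99%. Dividing the noncentralities by a residual variance of 0.91 (total SD 1, slope .3) gives 4% against 37%, and 21% against 70%. A separate simulation with its own assumptions gave 5% against 38%, and 22% against 70%. With no moderation, a per-exercise BF reaches 10 in under 0.1% of trials.

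**5. Precision of the contrast that answers the question.** The exercise effect at +1 SD minus that at −1 SD has standard error 2√(2/n): 0.138 residual SDs at 420 and 0.105 at 720. This is twice that of the main contrast (0.069 and 0.053).

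**The case against.** The strongest reply is that the plan already tests moderation properly. The interaction BF stands immediately before the read-out, with its own threshold, on a marker measured before randomisation. A reader might infer from the read-out that the trial would mistake a prognostic marker for an effect modifier. The documents do not support that: nothing says moderation is judged from within-condition differences, and in the no-moderation scenario the stated rule gives the right answer. This stands in full.

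The wording is also open to another reading. Stress differences for people at each neuroticism level could mean differences between conditions at that level. Against this, the sentence sets its comparison inside each condition. A reworded sentence settles it either way.

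A further temptation is to say that the planned output cannot identify the moderated exercise at all. That goes too far. Samples from an interaction model contain the slopes, and subtracting control's slope from an exercise's slope gives the estimate and its sign. What is missing is a stated commitment to do so.

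Three smaller points also stand. The plan does not say whether condition enters as one five-level factor, so the joint nature of the BF is the natural reading and not a certainty. The commitment "we planned to carry out four independent comparisons with the active controls" belongs to the confirmatory analysis and does not bind this one. The within-arm percentages rest on assumed correlations and are weak at 100 per arm when r = .2.

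**Conclusion.** The point holds in a limited form. The overall moderation test is sound. The read-out attached to it, as described, is prognostic and does not supply the exercise-specific effect by neuroticism level that the section's own question asks for. A single joint BF does not fill the gap, and under the BIC approximation it reaches 10 about 2% to 5% of the time at 420 per arm when one exercise's slope differs by 0.2, against roughly 31% to 38% for a BF on that exercise alone.

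The distinction between a within-arm gradient and a change in effect rests on no assumption. The percentages rest on the assumed correlations and slopes, equal arms and the BIC approximation; lmBF with its default priors would give other values. Importance is moderate at most: the analysis is exploratory, has no role in sampling and touches no confirmatory conclusion. The change is still worth making because it costs almost nothing.

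**What to change.** Keep the overall interaction BF and its threshold. Replace the last sentence of the moderation paragraph with text to this effect:

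*From the MCMC samples of the interaction model we estimate, for each exercise, the exercise-minus-control difference in STAI at the mean neuroticism score and at 1 SD below and above it, with 95% credible intervals. Moderation of an exercise is read from the change in this difference across neuroticism levels, not from differences between neuroticism levels within a condition.*

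This also defines low, average and high. In addition, report one interaction BF per exercise against control, labelled exploratory, and state that the overall BF comes from a single model with condition as a five-level factor, if that is the intention.

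The cost is one sentence, a few lines of code on samples already planned, and four more exploratory BFs to report. No new data are needed and the sampling plan is unchanged.

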We decided to set a series of rules to deal with careless or insufficient effort responders (C/IE; Currant, 2016), to reduce errors and provide more valid results. We decided to be conservative in our criteria by excluding participants that were providing too unrealistic answers that can hardly be due to casual errors, but at most to a consistent pattern in the response modality (i.e., finishing the survey as soon as possible to get payments/credits). Some possible issues were limited by some settings we fixed in the Qualtrics survey; we forced the answers for the questions connected to our exclusion criteria (meditation experience, english level, mental illnesses) for the questionnaires related to our dependent variables/moderator instead the answers were requested¹⁰.

To be sure that participants listened to the 15 minutes mindfulness/control condition we blocked the screen with the audio of the meditation/ control condition for 14 minutes (i.e., 840 seconds) so as not to allow participants to proceed to the following survey page until the meditation was actually finished. However, we excluded participants that completed the survey in less than 946 seconds, because as in addition to the 15 minutes of the recording we added a cut score for response time at 2 seconds an item, by following the recommendations of Huang et al., (2012)¹¹ To exclude participants that provided the same response to every question (i.e., selecting always the answer "strongly agree") we performed a long string analysis. Here we followed the recommendations of Huang et al., (2012) and we excluded from the study individuals with a string of consistent responses equal or greater than 10 (i.e., half of the length of the total scale). Furthermore If a participant responded to less than 50% of the items on a scale, we excluded that participant's score for that scale. Finally we decided not to exclude outliers as we believe that this would have led to the loss of important information and we did not perform any transformation of the data.

Ethics Information, Administrative Organization and Data protection

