The study received ethical approval from Swansea University while the sites that participated in the data collection received ethical approval from their local IRBs. To minimize the workload to collaborators, we provided an IRB submission pack that sites could adapt to their institutions' requirements. For most sites, only small adjustments to our IRB pack were necessary for submission. Each site's IRB protocols with ethics details and acceptance of each protocol can be found on the OSF project page at https://osf.io/6w2zm/.

¹⁰If participants do not provide any answer a message appears asking participants whether they want to continue to the following part of the survey without answering that particular question.

¹¹ We had 53 questions resulting in 103 seconds to be added to the 840 seconds of the meditation/control condition thus arriving at 946 seconds

Swansea University was the administrative organization for the study. Swansea University was also the data controller for this project. Personal data of participants were processed for the purposes outlined in the information sheet (see the document Information Sheet at https://osf.io/xuznc/). Standard ethical procedures involved participants providing their consent to participate in this study by completing the consent form that was administered at the beginning of the online survey used for the experiment.

We left each site the possibility to recruit participants in their preferred way. Participants could be recruited through the SONA system of the respective institution or via crowdsourcing platforms such as mTurk or Prolific academic. Participants could come from any geographic area if they met our inclusion criteria and could be given either credits or financial compensation in exchange for participation in the study.

Conflict of interests

The certified mindfulness instructor that collaborated on the multi-site project only recorded the meditations, but was not involved in the writing of any parts of the manuscript (e.g., choice of the analyses).

References

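### The page lock shows that the page stayed open, not that the recording was heard, and no other rule described in the plan measures listening

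*Combined protocol and SAP*

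**What the plan says.** The section on careless or insufficient effort responders gives the purpose of the lock: "To be sure that participants listened to the 15 minutes mindfulness/control condition we blocked the screen with the audio". The lock lasts 840 s and is there "so as not to allow participants to proceed to the following survey page until the meditation was actually finished". Under Procedure, "participants were presented with a different 15-minutes recording".

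The same section adds a minimum total time: "we excluded participants that completed the survey in less than 946 seconds". Footnote 11 builds that figure: "We had 53 questions resulting in 103 seconds to be added to the 840 seconds of the meditation/control condition". Two further rules concern answers: a long-string exclusion at 10 or more identical responses, and dropping a scale score when fewer than half its items are answered.

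Participants are asked to take part "using a smartphone with headphones or earphones attached, not a computer or laptop" and to sit somewhere quiet. The one related question described asks about the type of device. The plan itself names the motive of finishing fast for payment or credit, and the ethics section allows recruitment through SONA, mTurk or Prolific.

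The design analysis sets d = 0.20 as the effect to detect and mentions no allowance for non-listening. Under Confirmatory analyses, reaching the H0 boundary ends allocation to that exercise.

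**The concern.** A locked page is evidence about the page. It does not show that the audio was started, was audible or was attended to. Someone who puts the phone down, waits for the lock to open and then answers at a normal pace meets every rule described and is counted in the assigned arm. The time rule does not catch this person, because the wait itself supplies the 840 s.

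The lock also falls short of its second stated aim, since it opens before a 15-minute recording is over.

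At stake is the reading of a null result. An exercise can be closed at the H0 boundary because it does nothing, or because part of the arm did not hear it. For a self-administered recording that distinction matters, and nothing described in the plan would allow the two to be told apart.

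**Working it through.** **Timing.** The recording lasts 15 × 60 = 900 s (Procedure) and the lock 840 s, so the lock opens 900 − 840 = 60 s early. Footnote 11: 53 questions × 2 s = 106 s, and 840 + 106 = 946 s. The footnote prints 103 s, which would give 943 s. The main text describes the minimum as added to the full 15 minutes, which would give 900 + 106 = 1006 s. On the footnote's construction, the 946 s rule tests only the roughly 106 s of answering beyond the lock.

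**Room for a listening item.** Assuming 20 neuroticism items (the plan calls a string of 10 half the scale): 20 neuroticism + 20 STAI + 3 Manikin + 6 demographic + 3 eligibility + 1 device = 53, the stated count. This suggests, but does not prove, that the survey has no listening item.

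**Reproducing the design analysis.** Inputs: δ ~ N(0.20, 0.05), at most 720 per condition, stops at BF 10 or 1/10 (Bayesian design analysis); two-sided JZS test, r = √2/2 (Confirmatory analyses). With n per group and ν = 2n − 2,

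BF₁₀ = ∫ (1 + n g r²/2)^(−1/2) · [1 + t²/((1 + n g r²/2)ν)]^(−(ν+1)/2) · (2π)^(−1/2) g^(−3/2) e^(−1/(2g)) dg ÷ (1 + t²/ν)^(−(ν+1)/2).

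At n = 420 this gives an H1 stop at |t| ≥ 3.154 and an H0 stop at |t| ≤ 0.727; at n = 720 the limits are 3.225 and 1.03. With looks from 420 per group, every 10 per group, 20,000 simulated trials give H1 .718, H0 .068, maximum N .214 and average N 524. The plan states .72, .07, .21 and 526, so its figures reproduce.

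**Adding non-listening.** If a share p in each arm does not listen, and non-listeners have the same mean in both arms, the contrast becomes d × (1 − p): 0.20 × 0.9 = 0.18, 0.20 × 0.8 = 0.16, 0.20 × 0.7 = 0.14. The documents give no p; the values below are assumptions.

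| Assumed p | Contrast | Looks from 420: H1 / H0 | Looks from 100: H1 / H0 |
|---|---|---|---|
| 0% | 0.20 | .718 / .068 | .728 / .097 |
| 10% | 0.18 | .625 / .096 | .645 / .134 |
| 20% | 0.16 | .515 / .143 | .543 / .190 |
| 30% | 0.14 | .393 / .213 | .423 / .256 |

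A repeat with 60,000 runs came within .01 of every entry. The last column uses the start of monitoring given under Confirmatory analyses. Its higher H0 rate at 0% (.097 against .068) comes from the earlier start, not from non-listening. The plan looks every 3 days, so the spacing of 10 per group is also an assumption: from 100 per group at p = 0, spacings of 1 and 50 give .74/.11 and .71/.08.

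**Unequal shares.** The control is itself a recording. Let the story change stress by s among its listeners, relative to not listening, and the exercise by s − 0.20. The contrast is (1 − p_C)s − (1 − p_M)(s − 0.20). With s = −0.10:
- p_M = 10%, p_C = 30%: 0.7 × (−0.10) − 0.9 × (−0.30) = 0.20, not diluted.
- p_M = 30%, p_C = 10%: 0.9 × (−0.10) − 0.7 × (−0.30) = 0.12, diluted further than with equal shares.

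**The case against.** The hypothesis concerns participants allocated to a condition, so keeping non-listeners in their arm is the right analysis of it, and excluding them after randomisation could introduce bias. This stands.

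The plan nowhere says that d = 0.20 is an effect among people who heard the whole recording. If it is the difference between allocated groups, the stated .72 and .07 already include non-listening and nothing is lost. This stands too, and makes the figures above an illustration rather than an estimate.

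A reader might infer that every effect is diluted and every test pushed towards H0. The documents do not support that. It needs a true non-zero effect, similar non-listening in both arms and d = 0.20 read as the listeners' effect; the first unequal-share example leaves the contrast whole.

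A reader might also infer that the survey contains no listening check. The supportable statement is that the text describes none. The plan says that all study materials are on its OSF page, and the survey itself is not reproduced in the document.

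None of this rescues the claim that the lock makes listening sure, or that it holds people until the recording has finished.

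**Conclusion.** The point holds as a gap in measurement and an overstatement in wording, not as a flaw in the randomised comparison. On the plan's own text, the lock cannot establish listening, it opens 60 s before a 15-minute recording ends, and no other described rule detects silent waiting. An H0 stop would therefore be ambiguous between an ineffective and an unheard exercise.

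The size is conditional on three assumptions: an unknown non-listening share, equal shares in both arms, and d = 0.20 as the effect among listeners. Under them, each 10 points of non-listening costs roughly .09 to .12 of the probability of an H1 stop on the plan's own design analysis, and 10% to 30% raises wrong H0 stops from about .07 to between .10 and .21. The real share could be negligible; nothing described would show it. This merits a cheap improvement and does not invalidate the trial.

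**What to change.** 1. Before allocation, play a short clip with a spoken word that must be entered to continue. People without working sound then leave before randomisation, so the comparison is not biased.
2. After both the STAI and the Manikin, so that the outcomes are not disturbed, ask one listening item. Either put a spoken word, different from the first, into all seven recordings before minute 14 and ask for it, or, if re-recording is impractical, ask how much of the recording was played and heard, stating that the answer does not affect credit or payment. Exclude nobody on it, keep the as-allocated Bayes factor as confirmatory, and report the share by arm with the results.
3. Do not divide the difference by the share who listened. In the first unequal-share example the listeners' effect is 0.20, but the ratio gives 0.20/0.9 = 0.22 or 0.20/0.7 = 0.29, depending on whose share is used.
4. Set the lock to the full length of the recording, reconcile the main text with footnote 11, and recompute the minimum time for the lock and the added items. Replace the claim of assured listening with what the lock does: it keeps the page open for a set time.

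The cost is two survey items, a few people leaving before allocation, and a small update to the shared survey and the sites' ethics packs. A word in the recordings also means editing seven files and a slight interruption in each. With collection due to start on 23 March 2022, the day after pre-registration, the self-report version is the quicker one.
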